Neutrophil engraftment date	Post-transplant, once	This is defined as the first date on which the neutrophil count is $\geq 0.5 \times 10^9/L$ for at least 3 consecutive measures on different days. This date is generally noted in the chart as the date of neutrophil engraftment. The chart-noted date will be used to define the engraftment date.
Platelet engraftment date	Post-transplant, once	Collect from clinical chart. This is defined as the first date on which the platelet count is $20 \times 10^9/L$ for at least 3 consecutive measures on different days with no platelet transfusions in previous 7 days. This date is generally noted in the chart as the date of platelet engraftment. The chart-noted date will be used to define the engraftment date.
Chimerism with dates	Post-transplant, each instance	The percent chimerism will be collected with the corresponding cell type (for each cell type measured – RBC, CD34+ cells, mononuclear cells, T-cells, B-cells, granulocytes, and natural killer cells as reported).
Graft failure	Post-transplant	The diagnosis of graft failure with the date will be noted as such and may be qualified as primary or secondary. If noted in the chart, the primary or secondary nature should be noted.
GVHD prophylaxis	At time of transplant and ongoing throughout the study	Prophylaxis for GVHD will generally be provided with immunosuppressive medications. Each medication, dose, and dates of administration will be collected. Changes in the medications or decreases in dose will provide support for the requirement that patients have persistent HSCT-TMA despite modification of immunosuppression. The modification may occur prior to the chart diagnosis of HSCT-TMA because physicians react to changes in some measures (e.g., increasing LDH) while another measure (e.g., platelet count) has not become abnormal, delaying the diagnosis of HSCT-TMA.
Patient Status (with dates)		
Vital status	Last patient follow-up, once	Collect as the latest of 1) the last clinic visit or telephone contact with the patient at which the patient was alive or 2) the date of death.
Cause of death	Last patient follow-up, once	Collect for patients who have died. If no cause of death is recorded, the cause will be reported as unknown.
Date of death	Last patient follow-up, once	Collect for the patients who die.
Patient Relapse Status (with dates)		

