2.7. Handling of Missing Data

The following general methods will be used for producing the data summaries and the manner in which missing data will be documented:

- Available clinical data at each visit will be presented and the sample size displayed will reflect the patients with available data. Patient listings data will be provided as recorded on the case report form indicating partial dates and missing data.
- Generally, if data are missing or incomplete, the missing values will be indicated and incomplete values will be presented in the data listings. Analyses will be based on the observed data without imputation unless otherwise specified.

The TMA diagnosis date must have at least the month and the year. If the day is missing, the day will be imputed as 1.

Non-responder imputation will be used to handle missing data for the binary efficacy endpoints. Time-weighted average analysis and repeated measures models will be used to analyze the continuous secondary efficacy endpoints over time.

For patients whose death dates are incomplete, if only the day of the death date is missing, the day will be imputed as the first day of the month. If either the month or the year of the death date is missing, the death date will not be imputed, and the overall survival will be censored at the last known date of alive in the database. For the patients who are alive, overall survival will be censored at the last known date of alive in the database.

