2.8.2.2.2. Overall Survival

Overall survival will be calculated from the date of HSCT-TMA diagnosis. For the patients who are alive, their overall survival will be censored at the last known date of alive in the database. The method for handling a partially missing date of death is presented in Section 2.7.

Overall survival will be analyzed using Kaplan-Meier method by dose for the FAS population. Median overall survival and its 95% CI will be estimated by dose.

In addition, a competing risks analysis for overall survival will be performed. The cumulative incidence function of each pre-specified causes of death (GVHD, graft failure, infections, progression of underlying disease, HSCT-TMA, and others) will be estimated by nonparametric maximum likelihood method. The estimated cumulative incidence functions and their 95% CI will be displayed graphically.

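### SAP 2.7 censors a known death when its month or year is missing, which biases overall survival upward and drops the event from the cause-of-death curves

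*SAP*

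**What the plan says.** The rule in SAP 2.7 is introduced with "For patients whose death dates are incomplete, if only the day of the death date is missing", so it concerns patients recorded as dead. There are two cases:

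- **Day missing:** the day is set to the first of the month, and the death stays an event.
- **Month or year missing:** "If either the month or the year of the death date is missing, the death date will not be imputed". Survival time instead ends without an event on the last day the patient was recorded alive.

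The next sentence gives living patients the same treatment: "For the patients who are alive, overall survival will be censored at the last known date of alive in the database".

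SAP 2.8.2.2.2 adopts the rule by cross-reference: "The method for handling a partially missing date of death is presented in Section 2.7". It then states: "Overall survival will be analyzed using Kaplan-Meier method by dose for the FAS population". It adds: "In addition, a competing risks analysis for overall survival will be performed", with no separate rule for incomplete dates. The cause-specific cumulative incidence at 100 days (SAP 2.8.2.2.1) comes from that same analysis. SAP 2.8.2.2.5 repeats the survival analyses for responders and non-responders.

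No sensitivity analysis keeps these deaths as events, and Protocol 13.2.5.2 has no rule on incomplete death dates. The binary 100-day endpoint works the other way: a patient censored before day 100 is counted as dead.

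**The concern.** For these patients the event is known and only its date is uncertain. Kaplan-Meier estimation assumes that a censored patient has the same prospects as those still at risk. Here the patient is censored because of a death, so the assumption fails by construction. The rule also discards usable information, since the last date alive and any recorded year already bound the date.

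The bias favours the drug. Survival matters in this programme: Protocol 5.1 describes a comparison of survival with a literature-based historical control. Results are also reported by dose, and one dose group has only four HSCT-TMA patients.

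**Working it through.** **The plan's own figure.** The plan gives no figure for survival, deaths or incomplete dates. Its only precision figure is the exact 95% interval for a response rate with n = 28. Clopper-Pearson limits are the 2.5% quantile of Beta(x, 29−x) and the 97.5% quantile of Beta(x+1, 28−x). Over x = 0 to 28 the widths run from 12.34% to 38.71%, and x = 14 gives 30.65% to 69.35%. These match SAP 1.3 (12.3% to 38.7%; 30.6% to 69.4%) to rounding. They serve only as a yardstick: the half-width near 50% is (69.4 − 30.6)/2 = 19.4 points.

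**Inputs from the documents.** SAP Table 1 gives 2 + 22 + 4 = 28 HSCT-TMA patients, of whom 4 are at 370 mg.

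**Assumptions.** D = 10, 14 or 18 deaths, evenly spaced over days 30 to 600. All others are alive at day 730. Last contact is 15 days before death. One death lacks its month or year.

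**Formula.** With every death kept, 2-year survival is (28 − D)/28. If the affected patient is censored after j of the other deaths, the SAP rule gives (28 − j)/28 × (28 − D)/(27 − j). The extremes are j = 0, giving (28 − D)/27, and j = D − 1, giving (29 − D)/28.

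| Assumed deaths | Death kept | Earliest death recoded | Latest death recoded | Overstatement (points) |
|---|---|---|---|---|
| 10 | 18/28 = 64.3% | 18/27 = 66.7% | 19/28 = 67.9% | 2.4 to 3.6 |
| 14 | 14/28 = 50.0% | 14/27 = 51.9% | 15/28 = 53.6% | 1.9 to 3.6 |
| 18 | 10/28 = 35.7% | 10/27 = 37.0% | 11/28 = 39.3% | 1.3 to 3.6 |

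With 14 deaths and two recoded, the estimate is 14/26 = 53.8% to 16/28 = 57.1%. With one recoded, the median goes from 600 days to not reached. That jump is a knife-edge, because survival is exactly 50% in this example.

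**370 mg group.** With 4 patients and 2 assumed deaths, survival is 2/4 = 50%. Recoding the earlier death gives 2/3 = 67%; recoding the later gives 3/4 = 75%.

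**Direction.** From the true date of death onward the curve is never lower than with the death kept. Between last contact and death it can lie slightly below, because the risk set is one smaller. Compared with dating the death on the day after last contact, it is never lower at any time.

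**Cause of death.** Suppose 3 of 14 deaths are from HSCT-TMA. That cause's 2-year cumulative incidence is 3/28 = 10.7%, and all other causes total 11/28 = 39.3%. Recoding one HSCT-TMA death lowers the first to 7.1–7.4% and raises the second to 40.1–40.7%. In this layout one HSCT-TMA death falls on day 74. Recoding it takes that cause's 100-day incidence from 1/28 = 3.6% to 0.

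**Day 100.** In the 14-death layout two deaths precede day 100. If the first is recoded, Kaplan-Meier gives 26/27 = 96.3%. The binary rate stays at 26/28 = 92.9%.

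**The case against.** The strongest reply is that the rule may never be used. Date of death is its own item in Protocol 19.4, Table 2. Deaths must be reported within 24 hours of site awareness (Protocol 12.3.2), and missing data are queried (Protocol 15). This stands: nothing shows that any death date lacks its month or year. Against it, the SAP thought the case worth a rule, and the interim lock may come with queries still open (SAP 2.8.5).

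Overall survival is secondary and has no success threshold; the 15% criterion applies to response. That also stands. One patient's effect, at most 3.6 points, is small beside a half-width of about 19 points. But the interval conveys sampling error, and it does not disclose a shift in one known direction.

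Listings show partial dates as recorded (SAP 2.7), and adverse events leading to death are tabulated (SAP 3.4.1). The death therefore stays visible, but the survival estimate still omits it.

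A reader might infer more than the documents support:

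- **That 100-day survival is inflated.** The binary rate is not. Censoring before day 100 counts as death, and a last contact at or after day 100 is true 100-day survival.
- **That the SAP contradicts itself at day 100.** The binary rule treats any patient censored early as dead, including living patients lost to follow-up. Different results from the two methods are expected and are not specific to this rule.
- **That vital status was sought after patients left the site.** The documents describe medical records up to the last site contact or 104 weeks, whichever is earlier.
- **That Protocol 19.4 shows incomplete records of death dates.** Its sentence "If no cause of death is recorded, the cause will be reported as unknown" concerns a missing cause, not a missing date.

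**Conclusion.** The point holds as a defect in a stated rule. A patient known to be dead is analysed as a living one, the censoring is informative, and no other analysis restores the event. It affects Kaplan-Meier overall survival, the cause-of-death cumulative incidence (including at 100 days), and the survival analyses by response status. The primary endpoint and the binary 100-day rate are not inflated.

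The size is conditional. One affected patient among 28 adds about 1.3 to 3.6 points to 2-year survival if there are 10 to 18 deaths. In the 370 mg group with 2 deaths, it adds 17 to 25 points. The death counts, their timing and the number affected are all assumptions. The documents do not support a claim that the trial's survival results are in fact overstated.

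**What to change.** Replace the month-or-year clause in SAP 2.7 so that every known death is an event:

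- **Main analysis:** date the death at the earliest date consistent with the record, which is the day after the last date known alive, or 1 January of the recorded year if that is later. This follows the earliest-date convention that SAP 2.7 already uses for a missing day.
- **Sensitivity analysis:** use the latest consistent date, which is the earliest of the end of any recorded year, any documented date by which the death was known, and the data cutoff.
- **Elsewhere:** use the same dates in the competing-risks analysis, leave the binary 100-day rule unchanged, and report the number of patients affected.

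A midpoint between last contact and data cutoff would not be a safe substitute. Protocol 19.4 collects no date on which the death was first known, and the midpoint could ignore a recorded year. Take last contact on day 15, death on day 30 and an assumed cutoff at day 1500. The midpoint is (15 + 1500)/2 ≈ day 758, beyond 2 years. In the 14-death example that gives 15/28 = 53.6%, further from 50.0% than the 51.9% under the present rule.

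The cost is a few SAP sentences and a possibly slightly lower survival estimate. If no patient is affected, nothing changes.

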2.8. Statistical Assessment of the Study Objectives

2.8.1. Multiplicity Comparisons and Multiplicity

This is an uncontrolled study. No multiplicity adjustment will be performed.

2.8.2. Efficacy Analyses

2.8.2.1. Primary Efficacy Endpoint

A patient is a responder if this patient meets the responder criteria (Section 2.1) at any time post-baseline during the study. If a patient is not evaluable for a response criterion due to confounding factors, the non-evaluable response criterion will not be included in the determination of responder. Evaluability of each response criterion will be determined by a clinical review of relevant data and will be documented in the clinical study report. For example, potential confounding factors include graft failure for platelet count or transfusions, and nephrotoxic medications for renal function. Furthermore, laboratory values collected from both the local laboratories and the central laboratories will be used to determine response status.

Analysis of the primary efficacy endpoint will use a non-responder imputation to impute missing or incomplete data to evaluate response. The number and percent of responders will be summarized with exact 95% CI (Clopper-Pearson) by dose and total for the FAS and PAS

populations. If the lower bound of the exact 95% CI is greater than 15%, there is sufficient evidence to demonstrate efficacy of narsoplimab in the target patient population. Each criteria of the response will be listed for each patient.

Sensitivity analyses will include:

1. Subgroup analyses for the following subgroups will be performed for the FAS population:
 - Age (< 65 , ≥ 65 years)
 - Gender (Male or Female)
 - Graft-versus-host disease (GVHD) (Yes or No)
 - Significant infection (Yes or No)
 - Graft failure or non-engraftment (Yes or No)
 - Female-to-male transplant (Yes or No)
 - Multiple organ TMA involvement (Yes or No)
 - Mismatched donor (Yes or No)
 - Baseline platelet counts ($< 20,000$ or $\geq 20,000$ platelets/ μL)
 - Renal dysfunction at baseline (Creatinine $> \text{ULN}$ or spot urine protein $\geq 2+$ or > 30 mg/dL; Yes or No)
 - Any transfusions within the 2 weeks prior to or on the first OMS721 dose date (Yes or No)
2. A completer analysis will be performed using the patients with non-missing responses only. Exact 95% CI for the completer response rate will be provided for the FAS population by dose.
3. Two alternative definitions of response will be analyzed:
 - a. The first alternative response is defined as achieving an improvement in TMA markers and an improvement in renal function as defined in Section 2.1. The number and percent of the patients achieving the first alternative response will be summarized with exact 95% CI by dose for the FAS population.
 - b. The second alternative response is defined as the same as the primary endpoint by excluding the neurological function as defined in Section 2.1. The number and percent of the patients achieving the second alternative response will be summarized with exact 95% CI by dose for the FAS population.

In addition, individual patient plots of platelet count and LDH over time will be provided.

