[Khosla 2017]. Plasma therapy is thought to have no utility in this patient population [Khosla 2017, Rosenthal 2016]. Patients who do not respond to modification of their immunosuppression have a poor prognosis. Adult mortality has been reported to be as high as 100% (4 out of 4 patients, all of whom died within 69 days from diagnosis) [Worel 2007]. In a larger and more recent series, only 17% of adult patients (4 out of 24) who underwent immunosuppression modification and received treatment with plasmapheresis, defibratide, or rituximab survived 1 year [Bohl 2017]. Eculizumab has been reported to treat HSCT-TMA effectively with a 90% response rate when used off-label in 1 adult study; however, there was a high rate of infection-related mortality following eculizumab treatment [Bohl 2017]. These data demonstrate that HSCT-TMA is a life-threatening condition and, with the lack of effective treatment options, represents a significant unmet medical need.

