1, Cohort 3	3	4.0 mg/kg IV weekly x 4
2, Cohort 4 ^a	40 (aHUS)	4.0 mg/kg IV weekly x 12
3, Cohort 4 ^a	≤ 40 (aHUS)	4.0 mg/kg IV weekly x 12
2 ^b , Cohort 5	40 (TTP ^c /HSCT-TMA)	4.0 mg/kg or 370 mg IV weekly x 4
3 ^b , Cohort 5	≤40 (TTP ^c /HSCT-TMA)	4.0 mg/kg or 370 mg IV weekly x 4

Abbreviations: aHUS = atypical hemolytic uremic syndrome; HSCT-TMA = hematopoietic stem cell transplant-thrombotic microangiopathy; IV = intravenous.

^a As of Amendment 10, Cohort 4 was closed.

^b Doses for Stage 2 and Stage 3 were determined from Stage 1 PK, PD, and safety results. After Stage 1, this was 4 mg/kg. As of Amendment 10 of this protocol, the dose for HSCT-TMA patients was 370 mg IV weekly x 4. Any patients in the middle of treatment at the time of this protocol amendment remained on their original dose.

^c As of Amendment 10 of this protocol, enrollment of TTP patients was closed.

As of Amendment 11 of this protocol, enrollment in the study has been completed.

For patients with HSCT-TMA enrolled under Amendment 10 or earlier versions of this protocol, additional data will be collected. Notification and consent of patients (or legal representatives for deceased patients) for this additional data collection are being collected according to local rules and regulations.

These additional data are outlined in this amendment in Section 19.4. These data will include supplemental data on patient demographics and baseline conditions, donor characteristics, the transplant procedure, concomitant medications, TMA-related laboratory measures, transfusions, transplant complications, and outcomes. These data will be derived from medical records from the time of transplant conditioning through the last available patient contact with the site or up to 2 years (104 weeks) after the first OMS721 dose, whichever is earlier. These data were requested by regulatory authorities because patients who have undergone HSCT typically have complicated post-transplant courses, and these additional data will allow for better understanding of OMS721 response and outcomes. As of Amendment 11, enrollment in the study has been completed, and the additional data will be collected until a predetermined data cutoff date for those patients who have not reached 2 years after first OMS721 dose.

7.1.1. Stage 1

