8.3. Patient Withdrawal Criteria

8.3.1. Early Discontinuation of Study Drug Administration

Patients may voluntarily withdraw from the study at any time for any reason without prejudice to further treatment. A patient must permanently discontinue study drug under any of the following circumstances:

- The patient becomes pregnant. Study drug must be discontinued immediately and the pregnancy reported to the Sponsor.
- The patient wishes to discontinue study drug treatment for any reason.
- The patient experiences a medical emergency that necessitates discontinuing study drug treatment.
- The patient receives a prohibited concomitant therapy.
- The Investigator, Sponsor, or patient's primary care physician decides to discontinue treatment for medical reasons or due to the patient's noncompliance with the protocol.

The reason for termination of study drug before study completion must be recorded in the patient's Case Report Form (CRF). The patient should complete all scheduled study Follow-Up visits provided written consent to do so has not been withdrawn. Patients who discontinue study drug prematurely will not be replaced.

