10.2.2. Prohibited Concomitant Therapies

10.2.2.1. Eculizumab

If the Investigator decides to administer eculizumab, the patient should be withdrawn from the study.

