13.2.5. Efficacy Analyses

13.2.5.1. Analysis of Primary Efficacy Endpoint

A patient is a responder if this patient meets the responder criteria (Section 7.3) at any time post baseline during the study. If a patient is not evaluable for a response criterion due to confounding factors, the non-evaluable response criterion will not be included in the determination of responder. Evaluability of each response criterion will be determined by a clinical review of relevant data and will be documented in the clinical study report. For example, potential confounding factors include graft failure for platelet count or transfusions and nephrotoxic medications for renal function. Furthermore, laboratory values collected from both the local laboratories and the central laboratories will be used to determine response status.

Analysis of the primary efficacy endpoint will use a non-responder imputation to impute missing or incomplete data to evaluate response. The number and percent of responders will be summarized with exact 95% CI (Clopper-Pearson) by dose and total for the FAS and PAS populations. If the lower bound of the exact 95% CI is greater than 15%, there is sufficient

evidence to demonstrate efficacy of OMS721 in the target patient population. Each criteria of the response will be listed for each patient.

Sensitivity analyses will include:

- Subgroup analyses for the FAS population
- A completer analysis will be performed using the patients with non-missing responses only. Exact 95% CI for the completer response rate will be provided for the FAS population by dose.
- Two alternative definitions of response will be analyzed:
 - The first alternative response is defined as achieving an improvement in TMA markers and an improvement in renal function as defined in Section 7.3. The number and percent of the patients achieving the first alternative response will be summarized with exact 95% CI by dose for the FAS population.
 - The second alternative response is defined as the same as the primary endpoint by excluding the neurological function defined in Section 7.3. The number and percent of patients achieving the second alternative response will be summarized with exact 95% CI by dose for the FAS population.

In addition, individual patient plots of platelet count and LDH over time will be provided.

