Significant Adverse Events	Each instance	Collect events (with dates) requiring hospitalization or intervention with medication or procedures.
Concomitant Medications		
All immunosuppressives and changes	Each instance at onset	Collect the dates of initiation and discontinuation with each dose per administration. Collect changes in the dose per administration and frequency with dates.
All anti-infectives and changes	Each instance at onset	Collect the dates of initiation and discontinuation.
All cytotoxics	Each instance at onset	Collect the dates of initiation and discontinuation.
All targeted therapies	Each instance at onset	Collect the dates of initiation and discontinuation.
All growth factors	Each instance at onset	Collect the dates of initiation and discontinuation.

CONFIDENTIAL

No use, disclosure or reproduction outside of Omeros without prior written authorization

Variables	Timing/Periodicity of Data Collection	Data Collection Rules/Definitions
Eculizumab	Each instance at onset	Collect the dates of initiation and discontinuation.
Defibrotide	Each instance at onset	Collect the dates of initiation and discontinuation.
Investigational agents	Each instance at onset	Collect the dates of initiation and discontinuation.
Total parenteral nutrition	Each instance at onset	Collect the dates of initiation and discontinuation.
Ursodeoxycholic acid	Each instance at onset	Collect the dates of initiation and discontinuation.
Heparin	Each instance at onset only for VOD prophylaxis	Collect the dates of initiation and discontinuation.
Laboratory Measures		
Platelet count	See laboratory measure schedule ¹	Collect from the clinical chart. Overlapping data will also be available from the central laboratory on some dates.
Hemoglobin	See laboratory measure schedule ¹	Collect from the clinical chart. Overlapping data will also be available from the central laboratory on some dates.
White blood cell	See laboratory measure schedule ¹	Collect from the clinical chart. Overlapping data will also be available from the central laboratory on some dates.
Absolute neutrophil count	See laboratory measure schedule ¹	Collect from the clinical chart. Overlapping data will also be available from the central laboratory on some dates.
Lactate dehydrogenase	See laboratory measure schedule ¹	Collect from the clinical chart. Overlapping data will also be available from the central laboratory on some dates.

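### The primary response window has no cut-off when a new TMA-directed therapy starts: improvement after permitted therapies counts as OMS721 response, and scoring after eculizumab is ambiguous

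*SAP*

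**What the plan says.** **Response rule.** SAP 2.8.2.1: "A patient is a responder if this patient meets the responder criteria (Section 2.1) at any time post-baseline during the study". Protocol 13.2.5.1 has the same rule ("at any time post baseline during the study"). Neither document says when the study ends for this purpose.

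**Data that count.** SAP 2.8.2.1: "laboratory values collected from both the local laboratories and the central laboratories will be used to determine response status". Protocol 7.1 has supplementary chart data collected "through the last available patient contact with the site or up to 2 years (104 weeks) after the first OMS721 dose", whichever is earlier. The analysis windows in SAP 2.6 (Table 3) also run to Week 104.

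**Treatment and visits.** HSCT-TMA patients receive 4 weekly doses in Stage 2 and may receive 4 more in Stage 3. Their last scheduled visit is Day 92 (Protocol 7.1.2).

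**Other TMA therapy.** Eculizumab is the only prohibited therapy listed (Protocol 10.2.2). Plasma therapy is discouraged in HSCT-TMA but allowed (10.2.1.1). Protocol 5.1.2.3 names plasmapheresis, defibrotide and rituximab as treatments that have been used in this disease; none of them triggers withdrawal.

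**Eculizumab.** Protocol 10.2.2.1: "If the Investigator decides to administer eculizumab, the patient should be withdrawn from the study". Protocol 8.3.1 lists receipt of a prohibited therapy among the reasons to stop study drug permanently, and then adds: "The patient should complete all scheduled study Follow-Up visits provided written consent to do so has not been withdrawn". Protocol 19.4 applies chart collection to HSCT-TMA patients enrolled under Amendment 10 or earlier and makes no exception for those withdrawn. For eculizumab, defibrotide and investigational agents, its Table 2 says: "Collect the dates of initiation and discontinuation".

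**The concern.** The study has no control arm, so the responder proportion carries the efficacy claim. Both documents treat a lower exact 95% limit above 15% as sufficient evidence of efficacy. A patient who does not respond during 4 to 8 weeks of OMS721 can start another TMA treatment months later, improve on it, and meet the platelet, LDH and clinical criteria on chart values. If that counts, the proportion measures OMS721 plus whatever came after it. Crediting such improvement can add responders but cannot remove any, so the bias runs only towards meeting the 15% criterion.

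**Working it through.** **1. Is there a rule elsewhere that closes the window?**

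- *Non-responder imputation* (SAP 2.7, 2.8.2.1) covers missing or incomplete data. Values recorded after a new therapy are observed, so it does not apply to them.
- *The confounding-factor clause* (SAP 2.8.2.1) removes a non-evaluable criterion from the determination; it does not score the criterion as failed. Its examples are graft failure and nephrotoxic drugs, and it works by clinical review in an unblinded study.
- *The per-protocol set* (SAP 2.2) requires at least 28 days of treatment and says nothing about later therapy.
- *The sensitivity analyses* (SAP 2.8.2.1) are subgroups, completers and two alternative response definitions. None removes data after a new therapy.

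So for therapies that do not trigger withdrawal, later improvement counts as written. For eculizumab the answer depends on whether withdrawal under 10.2.2.1 ends the study for response purposes. The documents do not say, and 8.3.1 and 19.4 both point to data continuing.

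**2. Reproducing the plan's precision figures.** The sample size is n = 28 (SAP 1.3; SAP Table 1 gives 2 + 22 + 4 = 28 HSCT-TMA patients). For x responders, the Clopper-Pearson limits are:

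- lower = 0.025 quantile of Beta(x, n − x + 1)
- upper = 0.975 quantile of Beta(x + 1, n − x)

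Over x = 0 to 28 the interval width runs from 12.34% to 38.71%, and 14/28 gives 30.65% to 69.35%. These match the stated 12.3% to 38.7% and 30.6% to 69.4%.

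**3. Where the 15% criterion falls.** The last column is x − 8, the number of responders that would have to be rescored before the lower bound drops below 15%.

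| Responders of 28 | Rate | Lower bound | Rescored to lose success |
|---|---|---|---|
| 8 | 28.6% | 13.2% | already missed |
| 9 | 32.1% | 15.9% | 1 |
| 10 | 35.7% | 18.6% | 2 |
| 11 | 39.3% | 21.5% | 3 |
| 12 | 42.9% | 24.5% | 4 |
| 14 | 50.0% | 30.6% | 6 |

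**4. Effect on the error rate, by assumption.** Suppose true OMS721 response is 15%, and a share q of the remaining patients later meets the criteria on other therapy. The observed rate is then p = 0.15 + 0.85q, the expected number of extra responders is 28 × 0.85q, and success requires at least 9 of 28. The documents give no value for q.

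| q (assumed) | p | Extra responders expected | Chance of declaring efficacy |
|---|---|---|---|
| 0% | 15.0% | 0 | 1.8% |
| 5% | 19.25% | 1.2 | 7.4% |
| 10% | 23.5% | 2.4 | 19.3% |
| 20% | 32.0% | 4.8 | 56.4% |

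**The case against.** **Eculizumab.** A reader might infer that a patient who fails OMS721 and then improves on eculizumab is definitely scored as an OMS721 responder. The documents do not establish that. Response counts only within the study, and 10.2.2.1 withdraws such a patient. On that reading, later values fall outside the window and the patient would be a non-responder. The opposite reading is also open, because of 8.3.1 and 19.4. What stands is an ambiguity. The eculizumab rows in Table 2 do not settle it: chart collection starts at transplant conditioning, so they also capture use before enrolment, and collecting dates does not say how response is scored.

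**Other therapies.** OMS721 is meant to be used alongside standard of care, which must not be withheld. Response to OMS721 plus evolving care is therefore an arguable target, and scoring every new agent as failure changes that target and may understate the drug's effect. This supports exempting care already under way at first dose and still reporting the all-data rate. It does not support crediting OMS721 with improvement that first appears after a different TMA treatment, with no analysis that separates the two.

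**Size.** The number of switchers could be zero. The protocol reports that "Eculizumab has been reported to treat HSCT-TMA effectively with a 90% response rate when used off-label in 1 adult study", but nothing shows that this study used the same composite or enrolled patients who had failed OMS721, so the figure cannot be used to estimate how many responders rescue would add. A reader might also infer that a single rescued patient decides the trial. That is true only at exactly 9 of 28. At the plan's illustrative 50% response (14 of 28), six patients would have to be rescored.

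**Transparency.** Per-patient criterion listings, platelet and LDH plots and medication listings would let someone identify such cases afterwards. They do not change the reported rate.

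**Conclusion.** The point holds in a limited form: should-fix, with medium confidence. The primary rule has no end date and no event that closes it. For newly started therapies that do not trigger withdrawal, improvement afterwards counts as OMS721 response; for eculizumab, the documents leave the scoring undecided. The direction of bias is known (upward) but the size is not. Rescoring 1 to 4 patients changes the conclusion only if 9 to 12 responders are observed. These counts assume all 28 HSCT-TMA patients are analysed with both doses combined. The error-rate figures rest on assumed values of q and show sensitivity only; they do not estimate what happened. The plan's own precision figures are correct and unaffected.

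**What to change.** In SAP 2.8.2.1 and Protocol 13.2.5.1:

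- State that only data before the first dose of a newly started TMA-directed therapy count toward response, and that a patient who has not met all criteria by then is a non-responder.
- Fix the list of therapies, and the rule for deciding that a drug was given for TMA, before database lock and without reference to response.
- State that background standard of care already under way at the first OMS721 dose does not trigger the cut-off.
- Report the all-data rate alongside as a supplementary analysis.

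Separately, reconcile Protocol 10.2.2.1, 8.3.1 and 19.4 on whether, and for what purposes, a patient given eculizumab remains in the study. The change concerns scoring only and leaves patient care as it is.

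**Cost.** One analysis rule and one derived date per patient. Most of the dates are already collected under Protocol 19.4, which also plans to determine TMA treatment by reviewing concomitant medications and plasma therapy. The medication rows in Table 2 ask for dates and not for indication, so attributing a drug to TMA will need some review. The stated response rate may be slightly lower.
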